Data Management	See Electronic Signature Report _____ _____ Clinical Project Mgr. Data & Systems	_____ DATE
Reviewer	See Electronic Signature Report _____ _____ Fellow, Clinical Sciences	_____ DATE
Approver	See Electronic Signature Report _____ _____ Director, Clinical Sciences	_____ DATE

CHANGE HISTORY

Version	Originator	Description of Change(s) and Section Number(s) Affected	Date
1.0	[name]	Original Protocol	June 08, 2018
2.0	[name]	
• Updated [name]'s title under Authorized Signatures• Inclusion Criteria and Exclusion Criteria update to include numbered items from bullet points	June 13, 2018
3.0	[name]	
• Eliminated exclusion criteria #4: any previous or planned ocular surgery• 1.13 added worn lenses will be discarded	June 20, 2018

SYNOPSIS

Protocol Title	Contact Lens Insertion and Removal in a Senior Subject Demographic
Sponsor	JJVC, [name]
Clinical Phase	Development phase, Phase 1 (Pilot)
Trial Registration	This study will be registered on ClinicalTrials.gov by the Sponsor
Test Article(s)	ACUVUE OASYS® 1-DAY with HydraLuxe™ Technology
Wear and Replacement Schedules	Non-Dispensing
Objectives	This is a pilot study to evaluate the ability of a senior subject (60+ years of age) demographic to successfully insert and remove a contact lenses
Study Endpoints	Primary endpoint: 1. Overall success rate (as a percentage) of insertion and removal of a contact lens in both eyes
Study Design	This will be a pilot, one-visit, open-label, non-dispensing study.
Sample Size	A minimum of 12 and a maximum of 16 eligible subjects will be enrolled with approximately 50% with previous contact lens wear experience and approximately 50% with no previous contact lens wear experience.
Study Duration	This will be an open label, single visit, non-dispensing pilot study. After receiving instructions, subjects will attempt to insert and remove a contact lens in each eye. The study enrollment period will be approximately 3 weeks.
Anticipated Study Population	Healthy male and female volunteers (at least 60 years old) who are currently not habitual wearers of contact lenses (have not worn a contact lens in at least 5 years). At enrollment, approximately half of the subjects should be 60-65 years old and the other half should be 66 years old or older. Additionally, approximately half of the subjects should be neophytes (no previous lens wear experience) and the other half should have had previous lens wear experience at least 5 years prior to enrollment. Subject should have a spectacle astigmatism of ≤ 0.75 D in both eyes.

Eligibility Criteria	
Potential subjects must satisfy all the following criteria to be enrolled in the study:
 
Inclusion Criteria after Screening
 
 1. The subject must read, understand, and sign the STATEMENT OF INFORMED CONSENT and receive a fully executed copy of the form. 2. Appear able and willing to adhere to the instructions set forth in this clinical protocol 3. Must be at least 60 years of age at the time of screening 4. The subject must have normal eyes (i.e., no ocular medications or infections of any type). 
Inclusion Criteria after Baseline
 
 5. The subject must have best corrected visual acuity (BCVA) of 20/30 or better in each eye. 
Exclusion Criteria after Screening
 
Potential subjects who meet any of the following criteria will be excluded from participating in the study:
 
 1. A habitual and adapted wearer of contact lenses (have worn a contact lens at least one time in the past 5 years). 2. Currently pregnant or lactating (subjects who become pregnant during the study will be discontinued). 3. Any systemic disease, autoimmune disease, or use of medication that may interfere with contact lens wear. 4. Any ocular infection. 5. Any corneal distortion resulting from previous hard or rigid gas permeable contact lens wear. 6. Participation in any contact lens or lens care product clinical trial within 14 days prior to study enrollment. 7. History of binocular vision abnormality or strabismus. 8. Any infectious disease (e.g., hepatitis, tuberculosis) or a contagious immunosuppressive disease (e.g., HIV, by self-report). 9. Suspicion of or recent history of alcohol or substance abuse. 10. History of serious mental illness. 11. History of seizures. 12. Employee of investigational clinic (e.g., Investigator,
----------------------	--

	
Coordinator, Technician)
 
Exclusion Criteria after Baseline
 
13. Any ocular allergies, infections or other ocular abnormalities that are known to interfere with contact lens wear and/or participation in the study. This may include, but not be limited to entropion, ectropion, extrusions, chalazia, recurrent styes, glaucoma, history of recurrent corneal erosions, aphakia, or corneal distortion
 
14. Any Grade 3 or greater slit lamp findings (e.g., edema, corneal neovascularization, corneal staining, tarsal abnormalities, conjunctival injection) on the FDA classification scale
 
15. Any previous history or signs of a contact lens-related corneal inflammatory event (e.g., past peripheral ulcer or round peripheral scar), or any other ocular abnormality that may contraindicate contact lens wear.

Disallowed Medications/Interventions	Disallowed medications include any medication that may interfere with contact lens wear (at the investigator's discretion).
Measurements and Procedures	Lens insertion and removal
Microbiology or Other Laboratory Testing	None
Study Termination	The occurrence of one or more Unanticipated Adverse Device Effect (UADE), or any SAE where relationship to study agent cannot be ruled out, will result in stopping further dispensing investigational product. In the event of a UADE or SAE, the Sponsor Medical Monitor may unmask the treatment regimen of subject(s) and may discuss this with the Principal Investigator before any further subjects are enrolled.
Ancillary Supplies/ Study-Specific Materials	EyeCept
Principal Investigator(s) and Study Institution(s)/Site(s)	A full list of Principal Investigators, clinical sites, and institutions is kept separately from the Study Protocol and is included in the study Trial Master File.

Figure 1: Study Flowchart

n = 12-16 subjects

- Available powers: +1.00 D
- Males and females with normal eyes
- >60 years of age
- Half will have never worn contact lenses before (“neophytes”), other half will have worn previously but have discontinued for at least 5 years

**Informed Consent
Eligibility Criteria
Baseline Information**

- <0.75 D of cylinder
- 20/30 BCVA OD, OS, OU
- Subject must have normal eyes

Video Tutorial

- Subjects will watch the contact lens insertion and removal tutorial video

Trial Period

- Subjects will be given trial contact lenses and instructions by the technician on how to insert and remove them
- 20 minutes given for both insertion and removal attempts for both eyes = total trial time of 80 minutes
- Technician will record success or failure for insertion and removal for OD and OS

Final Evaluation

- Subject will fill out final evaluation form

COMMONLY USED ABBREVIATIONS AND DEFINITIONS OF TERMS

ADE	Adverse Device Effect
AE	Adverse Event/Adverse Experience
BCVA	Best Corrected Visual Acuity
BSCVA	Best Spectacle Corrected Visual Acuity
CFR	Code of Federal Regulations
COM	Clinical Operations Manager
CRA	Clinical Research Associate
CRF	Case Report Form
CRO	Contract Research Organization
CTP	Clinical Technical Procedure
D	Diopter
DMC	Data Monitoring Committee
eCRF	Electronic Case Report Form
EDC	Electronic Data Capture
FDA	Food and Drug Administration
GCP	Good Clinical Practice
HIPAA	Health Insurance Portability and Accountability Act
IB	Investigator's Brochure
ICF	Informed Consent Form
ICH	International Conference on Harmonization
IEC	Independent Ethics Committee
IRB	Institutional Review Board
ISO	International Organization for Standardization
JJVC	Johnson & Johnson Vision Care, Inc.
OD	Right Eye
OS	Left Eye
OU	Both Eyes
PD	Protocol Deviation
PI	Principal Investigator
PIG	Patient Instruction Guide
PQC	Product Quality Complaint
PRO	Patient Reported Outcome
QA	Quality Assurance
SAE	Serious Adverse Event/Serious Adverse Experience
SAS	Statistical Analysis System
SD	Standard Deviation
UADE	Unanticipated Adverse Device Effect
USADE	Unanticipated Serious Adverse Device Effect
VA	Visual Acuity

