5. TEST ARTICLE ALLOCATION AND MASKING

5.1. Test Article Allocation

This is a one-visit, non-randomized, open label pilot study. One test article (ACUVUE OASYS® 1-DAY with HydraLuxe™ Technology) will be used. No randomization scheme will be used.

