6.3. Administration of Test Articles

Test articles will be given to subjects meeting all eligibility requirements. Subjects will only be attempting to insert and remove test articles during the non-dispensing visit. Multiple test articles may be dispensed during the insertion and removal process if the lens needs to be replaced at the discretion of the Investigator due to excessive handling. Lost or damaged test articles may be replaced at the discretion of the Investigator and/or the Sponsor.

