11. STUDY TERMINATION

The occurrence of one or more Unanticipated Serious Adverse Device Effect (USADE), or any SAE where the relationship to study agent cannot be ruled out, may result in stopping further dispensing of test article. In the event of a USADE or SAE, the Sponsor may unmask the treatment regimen for the subject(s) and will discuss this with the Investigator before any further subjects are enrolled.

The Sponsor will determine when a study will be stopped. The Principal Investigator always has the discretion to initiate stopping the study based on patient safety or if information indicates the study's results are compromised.

JJVC reserves the right to terminate the study at any time for any reason. Additionally, the IEC/IRB reserves the right to terminate the study if an unreasonable risk is determined. The study can be terminated by the Principal Investigator at the individual clinical site due to specific clinical observations, if in their opinion, after a discussion with JJVC, it is determined that it would be unwise to continue at the clinical site.

JJVC (and the IEC/IRB and data monitoring committee [DMC], if applicable) will evaluate all adverse events. If it is determined that an adverse event presents an unreasonable risk, the investigation, or that part of the investigation presenting the risk, will be terminated, as soon as possible.

Should the study be terminated (either prematurely or as scheduled), the Investigator will notify the IEC/IRB and Regulatory Authority as required by local regulatory requirements.

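### The synopsis makes stopping further dispensing mandatory after a serious event that may be device-related; Section 11 makes it optional, and nothing says which governs

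*Combined protocol and SAP*

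**What the plan says.** The rule on stopping after a safety event appears in the Study Termination row of the synopsis and again in Section 11.

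- **Synopsis.** The trigger is one or more UADE, or an SAE of the following kind: "any SAE where relationship to study agent cannot be ruled out, will result in stopping further dispensing investigational product".
- **Section 11.** The trigger is one or more unanticipated serious adverse device effects (USADE), or an SAE of the same kind: "any SAE where the relationship to study agent cannot be ruled out, may result in stopping further dispensing of test article".

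The next sentence also differs. The synopsis has "In the event of a UADE or SAE, the Sponsor Medical Monitor may unmask the treatment regimen of subject(s) and may discuss this", naming the Principal Investigator as the other party and placing the discussion ahead of more enrollment. Section 11 has "In the event of a USADE or SAE, the Sponsor may unmask the treatment regimen for the subject(s) and will discuss this", naming the Investigator and giving the same timing.

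Section 11 then assigns authority: "The Sponsor will determine when a study will be stopped". On the site's side it adds a separate power: "The Principal Investigator always has the discretion to initiate stopping the study based on patient safety". It has one mandatory sentence of its own. If an adverse event is judged to present an unreasonable risk, the investigation, or the part that carries the risk, has to be terminated promptly.

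On design, Section 5.1 says "This is a one-visit, non-randomized, open label pilot study", with one lens product. Section 6.3 says "Test articles will be given to subjects meeting all eligibility requirements".

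**The concern.** A safety stop has to give one answer on the day it is needed. Suppose a subject has an SAE that the investigator rates as possibly related, a category that Section 13.2.1 describes as one where causality is not excluded. The next eligible subject is waiting. Under the synopsis, giving that subject a lens is barred. Under Section 11 it is allowed unless the sponsor or investigator decides otherwise.

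The site cannot tell whether going ahead would be a protocol deviation. Section 10 requires major deviations to be reported within 24 hours, and Section 17 has monitors check conduct against the protocol. The ethics committee would also be approving a protocol that contains two versions of one safety rule (Section 18.3). What is at stake is how the study is conducted, not any statistical result.

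**Working it through.** No figure in the plan is in question, so the check is mainly a comparison of texts.

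| Element | Synopsis, Study Termination | Section 11 |
|---|---|---|
| Device-effect trigger | UADE | USADE |
| SAE trigger | relationship not ruled out | relationship not ruled out |
| Consequence for dispensing | mandatory ('will') | discretionary ('may') |
| Discussion with the investigator | optional, by the Sponsor Medical Monitor | required, by the Sponsor |

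**1. Is the trigger the same?** The SAE limb has the same meaning in both places and carries the conflict alone. The device-effect labels differ, and the abbreviation list gives them separately. Section 13.1 defines only UADE, and defines it as a serious effect. Section 13.4.1 adds 'Serious' in brackets to the UADE label. The two terms largely coincide, but the point does not depend on that.

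**2. Does any text settle which version applies?** The change history (versions 1.0 to 3.0) records no change to either text, and there is no precedence rule. The sponsor's authority to decide when the study stops fits the discretionary version and does not reconcile it with the mandatory one. Section 11's compulsory termination sentence needs a prior finding of unreasonable risk. It therefore limits what Section 11 would tolerate, but it does not apply automatically to the shared trigger.

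**3. Does stopping dispensing mean anything in this study?** The synopsis, Section 4.1 and Section 6.3 call the study or visit non-dispensing. Yet Section 6.3 also speaks of lenses being dispensed during the insertion and removal attempts, Table 3 has a dispense column for the trial, and Section 7.2 heads Visit 1 as a dispensing visit. In this protocol the word covers giving lenses in the clinic, so the clause governs whether the next subject receives one.

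**4. Who is affected?** Section 8.2 already withdraws a subject whose serious event causes lens wear to be discontinued. The conflict concerns later subjects. Let N be the total enrolled (12 to 16, synopsis), let subjects be seen one after another, and let the event be in subject k and known before the next subject is seen:

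subjects still to be given lenses = N − k

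- N = 16: 16 − 1 = 15 at k = 1; 16 − 16 = 0 at k = 16.
- N = 12: 12 − 1 = 11 at k = 1; 12 − 12 = 0 at k = 12.

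**5. Is the discussion sentence a second conflict?** Read literally, what is to be discussed is the unmasking. Sections 5.1 to 5.3 describe an open-label, non-randomized study of one product, so there is nothing to unmask. The sentence is best treated as leftover text.

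**The case against.** The best case for leaving this alone is that it hardly matters. The lens is FDA-cleared and marketed (Section 1.3), is worn only at the site (step 1.11), and is used in one visit of about two hours (Table 3). Serious events reach the sponsor within 24 hours (Section 13.4.1), the investigator can initiate a stop at any time on safety grounds, and Section 11 compels termination once an unreasonable risk is found. All of this stands, and it is why the point is minor. None of it tells the site which version to follow before such a finding is made.

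A second objection is that nothing shows the mandatory version to be the intended one. That is correct. The sponsor's stated authority fits the discretionary version at least as well. A permanent automatic stop would also be hard to square with wording in both places that expects further enrolment. The remedy should therefore be a temporary hold that leaves the sponsor free to resume.

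A third objection is that an automatic consequence puts weight on the phrase about causality not being ruled out. Section 13.2.1 has an 'unlikely related' category as well as a 'possibly related' one, and the stopping text does not say which of them qualify. This is a fair caution for whoever redrafts the sentence, and it does not remove the conflict.

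A reader might also infer two contradictions, counting the discussion sentence, or might conclude that Section 11 already guarantees a review of the event before enrolment continues. The documents support neither. The sentence attaches to an unmasking step that has no content here, so it is neither a clear second conflict nor a secure existing duty.

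**Conclusion.** The point holds as an internal inconsistency in a safety rule: wrong as written, minor in severity. For an SAE whose relationship to the study agent cannot be ruled out, one current text requires dispensing to stop and the other only permits it, and nothing in the protocol chooses between them. The same applies to UADE and USADE to the extent that they are one category.

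No estimate, population or analysis is touched. The counts of 15 and 11 are ceilings. They assume sequential visits, an event in the first subject, and knowledge of it before the second is seen. A reader might take them as subjects put at risk, but they count only those to whom the choice of rule could apply. The documents give no probability of a qualifying event, and none is assumed. Nor do they support the inference that the study lacks protection after a serious event, since withdrawal, rapid reporting, investigator discretion and termination for unreasonable risk are all provided.

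**What to change.** Put one sentence in both the synopsis row and Section 11. Keep the existing trigger, use UADE in both places, and state that further dispensing of test article will be suspended until the Sponsor has reviewed the event with the Investigator and documented the decision to resume or terminate. Delete the unmasking and discussion sentence in both places. The sponsor's general authority, the investigator's discretion and the unreasonable-risk sentence in Section 11 can stay as they are.

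The edit is a few words. In substance, Section 11 loses the discretion to keep dispensing while an event is under review. The review before resuming becomes a new explicit duty and should be presented as such. A study of 12 to 16 subjects enrolling over about 3 weeks may be briefly paused. For scale, Section 13.4.1 allows the sponsor up to 10 working days to report its evaluation of a UADE. At 5 working days a week that is 10 / 5 = 2 weeks, so a hold that lasted the whole period would take up much of the enrollment window. The proposed hold is not tied to that limit and can end as soon as the decision is documented.

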1. INTRODUCTION AND BACKGROUND

In the spirit of addressing the unmet needs in a diverse population, J&J Vision would like to evaluate the potential opportunity of developing products that bring improvements in either vision and/or ocular health in a senior demographic. The purpose of this clinical trial is to

assess whether a senior subject population would have the interest and ability to successfully insert and remove a contact lens.

1.1. Name and Descriptions of Investigational Products

The test article will be senofilcon A contact lenses (ACUVUE OASYS® 1-DAY with HydraLuxe™ Technology).

1.2. Intended Use of Investigational Products

The intended use of the test article is for correcting refractive error. During the study, each test article will be inserted and then subsequently removed.

1.3. Summary of Findings from Nonclinical Studies

The test article will be an Food and Drug Administration (FDA)-cleared and marketed contact lens. For the most comprehensive nonclinical information regarding senofilcon A refer to the latest version of the package insert for this study.

1.4. Summary of Known Risks and Benefits to Human Subjects

For the most comprehensive risk and benefit information regarding the senofilcon A product refer to the latest version of the package insert.

1.5. Relevant Literature References and Prior Clinical Data Relevant to Proposed Clinical Study

See Package Inserts for ACUVUE OASYS® 1-Day. (APPENDIX C: PACKAGE INSERT (APPROVED PRODUCT).

2. STUDY OBJECTIVES, ENDPOINTS AND HYPOTHESES

2.1. Objectives

Primary Objective(s)

To evaluate the ability for a senior patient demographic to successfully insert and remove a contact lens.

2.2. Endpoints

Primary Endpoint(s)

Overall success rate (as a percentage) of insertion and removal of a contact lens in both eyes.

2.3. Hypotheses

Not Applicable.

3. TARGETED STUDY POPULATION

3.1. General Characteristics

The population to be studied will be healthy male and female volunteers (at least 60 years old) who are currently not habitual wearers of contact lenses (have not worn a contact lens in at least 5 years). At enrollment, approximately half of the subjects should be 60-65 years old and the other half should be 66 years old or older. Additionally, approximately half of the subjects should be neophytes (no previous lens wear experience) and the other half should have had previous lens wear experience but not within 5 years prior to enrollment. Subject should have a spectacle astigmatism of ≤ 0.75 D in both eyes.

3.2. Inclusion Criteria

Potential subjects must satisfy all of the following criteria to be enrolled in the study:

Inclusion Criteria after Screening

1. The subject must read, understand, and sign the STATEMENT OF INFORMED CONSENT and receive a fully executed copy of the form.
2. Appear able and willing to adhere to the instructions set forth in this clinical protocol
3. Must be at least 60 years of age at the time of screening
4. The subject must have normal eyes (i.e., no ocular medications or infections of any type).

Inclusion Criteria after Baseline

5. The subject must have best corrected visual acuity (BCVA) of 20/30 or better in each eye.

3.3. Exclusion Criteria

Potential subjects who meet any of the following criteria will be excluded from participating in the study:

1. A habitual and adapted wearer of contact lenses (have worn a contact lens at least one time in the past 5 years).
2. Currently pregnant or lactating (subjects who become pregnant during the study will be discontinued).
3. Any systemic disease, autoimmune disease, or use of medication that may interfere with contact lens wear.
4. Any ocular infection.
5. Any corneal distortion resulting from previous hard or rigid gas permeable contact lens wear.
6. Participation in any contact lens or lens care product clinical trial within 14 days prior to study enrollment.

7. History of binocular vision abnormality or strabismus.
8. Any infectious disease (e.g., hepatitis, tuberculosis) or a contagious immunosuppressive disease (e.g., HIV, by self-report).
9. Suspicion of or recent history of alcohol or substance abuse.
10. History of serious mental illness.
11. History of seizures.
12. Employee of investigational clinic (e.g., Investigator, Coordinator, Technician)

Exclusion Criteria after Baseline

13. Any ocular allergies, infections or other ocular abnormalities that are known to interfere with contact lens wear and/or participation in the study. This may include, but not be limited to entropion, ectropion, extrusions, chalazia, recurrent styes, glaucoma, history of recurrent corneal erosions, aphakia, or corneal distortion
14. Any Grade 3 or greater slit lamp findings (e.g., edema, corneal neovascularization, corneal staining, tarsal abnormalities, conjunctival injection) on the FDA classification scale
15. Any previous history or signs of a contact lens-related corneal inflammatory event (e.g., past peripheral ulcer or round peripheral scar), or any other ocular abnormality that may contraindicate contact lens wear.

